6.3.3 Third Primary Estimand

Primary Objective 2: To assess the safety of FTC/TDF for PrEP during pregnancy and postpartum by comparing pregnancy outcomes and maternal and infant safety between cohorts.	
Estimand description	The probability of an adverse pregnancy outcome among HIV-uninfected pregnant women who are PrEP exposed compared to women who are PrEP unexposed during pregnancy.
Treatment	
 1. Daily oral PrEP (200 mg FTC/ 300 mg TDF) throughout follow-up. 2. Enhanced adherence support, including SMS messaging and feedback of drug levels with tailored counseling. 3. Behavioral HIV risk reduction package
Target population	Analysis set Women who are pregnant and HIV-uninfected, 16-24 years of age, with a confirmed singleton pregnancy of 32 weeks' gestation or less and who have access to a mobile phone and are able to receive and read SMS messages
Variable(s)	Outcome measure(s) Composite adverse pregnancy outcomes of 
 • Spontaneous abortion (occurring at <20 weeks gestation) • Stillbirth (occurring at ≥20 weeks gestation) • Preterm delivery (<37 completed weeks' gestation) • Small for gestational age (<10th percentile using INTERGROWTH-21st norms and ultrasound derived gestational age at delivery)
Handling of intercurrent events	Handling of missing data • Failure to start PrEP (in Cohort 1 or Cohort 2/Step 2) (Treatment policy strategy) • Premature discontinuation of PrEP during pregnancy (Treatment policy strategy)
Population-level summary measure	Analysis approach Odds ratio of an adverse pregnancy outcome among PrEP exposed women during pregnancy vs. adverse pregnancy outcomes among PrEP unexposed women in pregnancy

Supplemental Analyses:

- Univariable and multivariable logistic regression methods will be used to evaluate associations of PrEP use and the composite outcome indicating presence vs. absence of any adverse pregnancy outcomes, controlling for potential confounders. The same analyses will be conducted for each of the pregnancy outcomes which comprise the

composite outcome separately. Analyses of small-for-gestational age births will be restricted to live births.

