## 3.2 PrEP Comparison Component Study Design

The PrEP Comparison Component will assess feasibility, acceptability, adherence to, and safety of PrEP during pregnancy and postpartum in HIV-uninfected adolescents and young women. Women will be enrolled prior to 32 weeks' gestation in two cohorts: those who agree to initiate PrEP (Cohort 1) and those who decline (Cohort 2). Infants will be enrolled *in utero* at the same time the woman is enrolled. A randomized trial in which one arm would not receive PrEP would be unethical at this time due to the overwhelming evidence supporting the efficacy of PrEP to prevent HIV infection (172). All women enrolled in the study will receive a standard of care package of HIV prevention services and a study-specific behavioral risk reduction intervention. Additionally, all women will receive support for antenatal, delivery and early infant care through

one-way mHealth messaging services. Women who choose to initiate PrEP will be provided PrEP as well as a study-specific adherence support intervention.

Regardless of cohort, all maternal participants will follow similar schedules of evaluations through the course of pregnancy and in the 26 weeks following delivery. Following Cohort 2 provides an opportunity to document the process of decision-making around HIV prevention during this time of substantial risk; as these women may choose to initiate PrEP at any stage following study entry, triggers for change in PrEP perceptions and acceptability over time will be recorded to better understand women's motivation to seek additional HIV prevention (see [Section 3.2.1](#)) services. As Cohort 2 is not exposed to antiretroviral agents during pregnancy or postpartum, the study will also obtain preliminary safety data for TDF use in HIV-uninfected women during this period. Cohort 2 will serve as a comparison group for estimates of incidence and prevalence of maternal and infant safety outcomes including a) pregnancy outcomes, b) maternal adverse events, and c) infant growth and development between the two cohorts (see [Section 9.2.2](#)). The primary analysis will be based on original Cohort designation at baseline. Additional secondary analyses that consider the population of women who may initially decline PrEP and then later decide to initiate it will be considered, refer to [Section 9](#).

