#### **Primary Objective 2.3.2:**

*Analyses of adverse pregnancy outcomes:* The proportion of women in Cohort 1 and Cohort 2 with adverse pregnancy outcomes (a composite indicator defined as at least one of the following: spontaneous abortion (occurring at <20 weeks gestation), stillbirth (occurring at  $\geq 20$  weeks gestation), preterm delivery (<37 completed weeks gestation), or small for gestational age (<10th percentile using INTERGROWTH-21st norms and ultrasound (US)- derived gestational age at delivery) will be estimated and compared. Univariable and multivariable logistic regression methods will be used to evaluate associations of PrEP use and the composite outcome indicating presence vs. absence of any adverse pregnancy outcomes, controlling for potential confounders. The same analyses will be conducted for each of the pregnancy outcomes which comprise the composite outcome separately.

*Analyses of maternal adverse events and infant adverse events:* Cumulative rates of maternal adverse events and infant adverse events will be compared, respectively, in Cohort 1 and Cohort 2. Where appropriate, there will be stratification according to time period (i.e., antepartum (AP) and postpartum (PP), and within AP by gestational age category of enrollment). Maternal adverse events will be considered separately from infant adverse events. Cox proportional hazards regression will be used to evaluate differences in the rate of adverse events in the two cohorts. For the maternal adverse events, among women in Cohort 1, person time will begin accruing when PrEP is initiated and for women in Cohort 2 it will begin accruing after study entry. Rates of maternal and infant adverse events in AP and PP periods will also be calculated and compared across levels of PrEP adherence (based on TFV-DP levels in DBS). Models will be fit adjusting for potential confounders.

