Regardless of cohort, all maternal participants will follow similar schedules of evaluations through the course of pregnancy and in the 26 weeks following delivery. Women in Cohort 2 may choose to initiate PrEP at any stage following study entry, and triggers for change in PrEP perceptions and acceptability over time will be recorded to better understand women's motivation to seek additional HIV prevention services. As Cohort 2 is not exposed to antiretroviral agents during pregnancy or postpartum, its unexposed time period will serve as a comparison group for estimates of incidence and prevalence of maternal and infant safety outcomes including a) pregnancy outcomes, b) maternal adverse events, and c) infant growth and development between the two exposure groups.

The primary objectives focus on women who initiate PrEP during pregnancy and continue through the first 26 weeks postpartum (Cohort 1). Adherence to PrEP will be assessed by measuring TFV-DP drug levels in dried blood spots. Participants in this arm will receive an intervention designed to provide participant-centered support, including support for PrEP use/adherence, comprised of a) two-way SMS messaging related to PrEP adherence, and b) targeted adherence counseling guided by TFV-DP drug levels.

Maternal participants who change their intent regarding PrEP will be allowed to do so. Participants in Cohort 1 who choose to stop PrEP will continue in follow-up. Maternal participants

in Cohort 2 who subsequently choose to initiate PrEP will undergo a Step Change, and will be referred to as Cohort 2/Step 2 and will follow the procedures for Cohort 1/Cohort 2 Step 2. While a formal step change will only be required when those originally declining PrEP later chose to initiate it, there is no upper limit set on the number of switches allowed for each participant. Switching will be closely monitored as part of feasibility and adherence outcomes.

There will be no randomization for this study. To monitor the balance of the maternal participants enrolled among various groups, the enrollment will be stratified by:

- Cohort: PrEP vs. No PrEP at enrollment
- Trimester of enrollment during pregnancy: 1st or 2nd trimester vs. 3rd trimester
- Country
- Age at enrollment: 16-17 years vs. 18 years of age and older

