6.3.2 Second Primary Estimand

Primary Objective 2: To assess the safety of FTC/TDF for PrEP during pregnancy and postpartum by comparing pregnancy outcomes and maternal and infant safety between cohorts.	
Estimand description	Incidence rate ratio of cumulative adverse events (AEs) up to 26 weeks postpartum among PrEP exposed vs. PrEP unexposed women
Treatment	
 1. Daily oral PrEP (200 mg FTC/ 300 mg TDF) throughout follow-up. 2. Enhanced adherence support, including SMS messaging and feedback of drug levels with tailored counseling. 3. Behavioral HIV risk reduction package
Target population	Analysis set
Women who are pregnant and HIV-uninfected, 16-24 years of age, with a confirmed singleton pregnancy of 32 weeks' gestation or less and who have access to a mobile phone and are able to receive and read SMS messages	Maternal Safety Set: all enrolled maternal participants
Variable(s)	Outcome measure(s)
Occurrence of at least one of the following maternal AEs up to 26 weeks postpartum 
 • Grade 3 or higher adverse events • Grade 2 or higher chemistry abnormalities 	Outcome measures as defined by the variables (graded according to the NIAID DAIDS Table for Grading the Severity of Adult and Pediatric Adverse Events). 
 • The start of person-time for the PrEP-exposed group is study entry for Cohort 1 and Cohort 2/Step 2 entry for Cohort 2; • The start of person-time for the PrEP unexposed group is study entry (for Cohort 2 only; person-time is censored when initiating PrEP for participants enrolled in Cohort 2/Step 2)
Handling of intercurrent events	Handling of missing data

 • Failure to start PrEP (in Cohort 1 or Cohort 2/Step 2) (Treatment policy strategy) • Premature discontinuation of PrEP (Treatment policy strategy) 	Participants who discontinue follow-up before the 26-week postpartum visit will have their outcome determined based on data available until the time of discontinuation (i.e., a participant who discontinued follow-up without a prior AE is assumed not to have an AE had they been observed for the intended duration).
Population-level summary measure	Analysis approach

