Incidence rate ratio (among PrEP exposed vs. PrEP unexposed women) of cumulative adverse events up to 26 weeks postpartum	Incidence rate ratio of cumulative AEs up to the week-26 postpartum visit (among PrEP exposed vs. PrEP unexposed women) estimated based on Poisson distribution (with 95% Wald CI).

Supplemental Analyses:

- Analyses will be repeated stratified by time period (i.e., antepartum (AP) and postpartum (PP), and within AP stratified by gestational age category of enrollment).
- Rates of maternal adverse events in AP and PP periods will also be calculated and compared across levels of PrEP adherence (based on TFV-DP levels in dried blood spots). Models will be fit adjusting for potential confounders.

- To compare time to first adverse event in PrEP exposed vs. PrEP unexposed women, the hazard ratio (95% CI) will be estimated with Logrank test p-value from Cox proportional hazards regression on time to first AE with PrEP exposure as a time-varying covariate.

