6.3.5 Fifth Primary Estimand

Primary Objective 2: To assess the safety of FTC/TDF for PrEP during pregnancy and postpartum by comparing pregnancy outcomes and maternal and infant safety between cohorts.	
Estimand description	Difference in mean infant growth and development outcomes at birth and age 26 weeks among PrEP exposed and PrEP unexposed infants;
Treatment	Infants exposed to the following maternal treatment in utero and/or through breastfeeding: 
1. Daily oral PrEP (200 mg FTC/ 300 mg TDF) throughout follow-up.2. Enhanced adherence support, including SMS messaging and feedback of drug levels with tailored counseling.3. Behavioral HIV risk reduction package
Target population	Analysis set
Infants born to women who are pregnant and HIV-uninfected, 16-24 years of age, with a confirmed singleton pregnancy of 32 weeks' gestation or less and who have access to a mobile phone and are able to receive and read SMS messages	Infant Safety Set: growth and development Infants of women who have ever used PrEP (in Cohort 1 or Cohort 2 Step 2) will be considered PrEP exposed. Infants of women who have never used PrEP will be considered PrEP unexposed. If PrEP exposure occurs prior to the outcome measurement of interest then the infant will be considered PrEP exposed.
Variable(s)	Outcome measure(s)
Infant growth and development outcomes	The following will be calculated to evaluate infant safety outcomes: 
• Infant bone mineral content (grams) by dual energy X-ray absorptiometry (DXA) scan of the whole body (WB-BMC) at birth and lumbar spine (LS-BMC) at birth and 26 weeks• Infant creatinine and CrCl rate measured by Schwartz equation at birth and at 26 weeks• Infant length-for-age z-score at birth and at 26 weeks The week 26 measurement will be at the Week 26 study visit

Handling of intercurrent events	Handling of missing data

• Mother's failure to start PrEP (in Cohort 1 or Cohort 2/Step 2) (Treatment policy strategy)• Mother's discontinuation of PrEP (Treatment policy strategy)	Sensitivity analysis: for infants discontinuing study prior to the 26 weeks of age, use the last value carried forward for the 26 weeks visit.
Population-level summary measure	Analysis approach

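### The SAP's pregnancy-outcome odds ratio appears to count antenatal Step 2 women as PrEP exposed, which departs from the protocol's baseline-cohort comparison and lets immortal time pull the estimate towards safety

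*SAP*

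**What the plan says.** SAP 6.3.3 (Third Primary Estimand) gives each woman one binary outcome, the composite of spontaneous abortion, stillbirth, preterm delivery and SGA. Its summary measure is "Odds ratio of an adverse pregnancy outcome among PrEP exposed women during pregnancy vs. adverse pregnancy outcomes among PrEP unexposed women in pregnancy". Its intercurrent-event row reads "Failure to start PrEP (in Cohort 1 or Cohort 2/Step 2) (Treatment policy strategy", which names Step 2 women alongside Cohort 1. SAP 2.1.2 says "Women in Cohort 2 may choose to initiate PrEP at any stage following study entry" and takes the unexposed time of Cohort 2 as the comparator, pregnancy outcomes included. SAP 2.3.3 words the safety objective as exposed against unexposed groups. For infant growth, SAP 6.3.5 states an ever-used rule: "Infants of women who have ever used PrEP (in Cohort 1 or Cohort 2 Step 2) will be considered PrEP exposed", provided that exposure precedes the measurement.

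For maternal adverse events, SAP 6.3.2 splits follow-up at the switch: "person-time is censored when initiating PrEP for participants enrolled in Cohort 2/Step 2". It adds a Cox model "with PrEP exposure as a time-varying covariate". SAP 6.3.4 does the same for infant adverse events.

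The protocol differs. Section 3.2 says "The primary analysis will be based on original Cohort designation at baseline" and leaves women who start later to additional secondary analyses. Section 9.2.6, Primary Objective 2.3.2, plans to estimate and compare "The proportion of women in Cohort 1 and Cohort 2 with adverse pregnancy outcomes".

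**The concern.** A Cohort 2 woman can move to the exposed side of this comparison only while she is still pregnant. Each further week of pregnancy gives her more opportunity. Counseling of women not on PrEP ends by asking about interest in starting (Protocol 5.3.2), antepartum visits run at Weeks 4, 8, 12, 24 and 36, and the step change takes two visits. A pregnancy that ends early, by loss or preterm delivery, leaves less time to switch and tends to stay in the unexposed group. A pregnancy that reaches term has the most time to be reclassified.

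The exposed group therefore gains women selected for not yet having had the outcome, and the unexposed group keeps those who had it early. With no drug effect at all, the odds ratio falls below 1. In a primary safety comparison this is the unhelpful direction. The supplemental logistic models adjust for confounders, and that does not remove immortal time.

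**Working it through.** **Plan's own figure.** Protocol Table 10 gives the differences detectable with 80% power for 100 against 200 women at alpha 0.05. A two-proportion calculation (pooled variance, two-sided 0.05 assumed, no continuity correction) gives power 0.806 for 10% vs 23%. For the 20% row, the stated odds ratio of 2.19 implies 35.4% and gives 0.797. The table reproduces and is not affected by this point. The documents give no figure for antenatal switching.

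**Two-by-two arithmetic, no PrEP effect.** Inputs: 200 and 100 women (Protocol 9.2.4); risk p = 20%, borrowed for illustration from the monitoring trigger in SAP 2.5 (it is not a stated background rate); s Cohort 2 women switch before delivery; their risk is r times the cohort risk.

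- Exposed events: a = 200p + s·r·p, among 200 + s women.
- Unexposed events: b = 100p − s·r·p, among 100 − s women.
- OR = [a/(200 + s − a)] / [b/(100 − s − b)].

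Results:

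- s = 10, r = 0.75: a = 41.5, b = 18.5; (41.5/168.5)/(18.5/71.5) = 0.95.
- s = 20, r = 0.75: a = 43, b = 17; (43/177)/(17/63) = 0.90.
- r = 1: OR = 1.00, so no bias.

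**How far r falls below 1.** Pregnancies were simulated with no PrEP effect and a constant switching rate in Cohort 2, under two sets of assumptions. Set A: entry at 14-32 weeks, loss 2%, preterm 12-15%, SGA 10-20%. Set B: entry at 14-32, 20-32 or 14-24 weeks, loss 2-3%, preterm 11%, SGA 12%. In set B, switchers' risk relative to the cohort was 0.83-0.88 for the composite, 0.65-0.75 for loss or preterm delivery, and 1.00-1.03 for SGA. Putting r = 0.85 and s = 20 into the formula gives (43.4/176.6)/(16.6/63.4) = 0.94, in line with the simulated composite.

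| Cohort 2 starting PrEP before delivery (assumed) | Composite, A | Composite, B | Preterm alone, A | Preterm alone, B | Loss or preterm, B |
|---|---|---|---|---|---|
| 10% | 0.97-0.98 | 0.97-0.98 | 0.95 | 0.95-0.96 | 0.95-0.96 |
| 20% | 0.93-0.95 | 0.94-0.95 | 0.90 | 0.89-0.93 | 0.88-0.91 |
| 30% | 0.90-0.92 | 0.90-0.92 | 0.85 | 0.84-0.90 | 0.83-0.86 |

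In set B the SGA odds ratio stayed at 0.997-1.017. Classifying by entry cohort gave 0.997-1.007 for the composite, which is no bias within simulation error.

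**Size against precision.** At 20% risk in both groups, the SE of the log odds ratio is √(1/40 + 1/160 + 1/20 + 1/80) = 0.306. With ln(0.94) = −0.062, the bias at 20% switching is about one-fifth of an SE.

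**Cost of the entry-cohort comparison.** Suppose the true risks are 20% unexposed and 35% exposed (OR 2.15), with 20% switching.

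- Full drug effect in switchers: Cohort 2 risk is 0.8 × 20% + 0.2 × 35% = 23%, so the entry-cohort OR is (0.35/0.65)/(0.23/0.77) = 1.80. Ever-exposed classification with r = 0.85 gives exposed events 70 + 20 × 0.2975 = 75.95 of 220 and unexposed events 16.6 of 80: OR 2.01.
- Half the excess risk (27.5%): the entry-cohort OR is 1.97 and the ever-exposed OR 1.96.

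**The case against.** **The rule is inferred.** A reader might take 6.3.3 to state that a mid-pregnancy starter is exposed for her whole pregnancy. It does not. The Step 2 wording there is an intercurrent-event rule, the table's objective row still speaks of cohorts, and coding detail is left to the Analysis Implementation Plan. The contents of the analysis-set, missing-data and analysis-approach cells of 6.3.3 are also missing from the text available here, so nothing can be argued from their silence. This stands. The inference is nevertheless firm, because SAP 2.1.2, 2.3.3 and 6.3.5 all group by exposure and one odds ratio per woman cannot split a pregnancy at the switch.

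**Net direction.** A reader might also infer that PrEP will look safer than it is overall. The documents do not support that. Protocol 9.2.1 itself suggests that women in serodiscordant relationships may be readier to start PrEP and at higher risk of adverse pregnancy outcomes, which would push the other way. Only the immortal-time part has a known sign.

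**Size.** Cohort 2 women state at entry that they are unwilling to take PrEP (Protocol 4.2.1.11), the step change has laboratory criteria, and postpartum starts do not touch this outcome. Switching may be rare. Up to 20% switching, the composite bias is small beside a detectable odds ratio of about 2.2 at a 20% background. This stands too, although 6.3.3 also analyses each component separately, and the pull on preterm delivery is larger.

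**Dilution.** Entry-cohort classification can hide more of a true harm than the bias it removes: 1.80 against 2.01 when the truth is 2.15, in the full-effect example. That is correct, and is why it should not be reported alone.

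**Conclusion.** The point holds as a departure from the protocol that brings in an avoidable bias. The SAP appears to replace the protocol's Cohort 1 vs Cohort 2 comparison with an exposure grouping that contains immortal time, although it handles the same switch by splitting person-time in 6.3.2 and 6.3.4.

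Under no PrEP effect, the expected composite odds ratio is about 0.97-0.98 at 10% antenatal switching, 0.93-0.95 at 20% and 0.90-0.92 at 30%. For preterm delivery, or loss and preterm together, it is about 0.95, 0.90 and 0.85. SGA is essentially unaffected. These figures assume a constant switching rate unrelated to risk, together with the stated entry and event-rate ranges; the switching percentages are assumptions. If few women switch before delivery, the effect is negligible. The change is worth making because the pull is towards no harm in a primary safety comparison and the protocol's own analysis avoids it.

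**What to change.** 1. In SAP 6.3.3, make Cohort 1 vs Cohort 2 at study entry the primary comparison for the composite and its components, in line with Protocol 3.2 and 9.2.6. Keep women who step up during pregnancy in Cohort 2, and state this classification rule in words.
2. For loss and preterm delivery, add a time-to-event model on gestational age, with delayed entry at enrollment and PrEP as a time-varying covariate that changes at Step 2 entry, as the SAP already does for adverse events. Report it beside the primary result.
3. Report the number of antenatal Step 2 entries and the gestational age at each, so that readers can judge how much either problem matters.

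The cost is SAP wording, one extra model and one short table; no new data collection is needed beyond Step 2 dates and ultrasound-based gestational age. The real downside is the dilution shown above, which grows with the number of switchers and with the drug effect they receive. The time-varying model is the answer to it for loss and preterm delivery.

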## **4.2 PrEP Comparison Component (Cohorts 1 and 2)**

### **4.2.1 Inclusion Criteria**

Mothers must meet all the following criteria prior to study entry to be included in this component.

- 4.2.1.1** At study entry, mother is 16-24 years of age.
  - *For mothers who are of legal age to provide independent informed consent as determined by site SOPs and consistent with site IRB/EC policies and procedures:* The mother is willing and able to provide written informed consent for her and her infant's study participation.
  - *For mothers who are not of legal age to provide independent informed consent.* The parent/guardian or other legally authorized representative of the mother and her infant is willing and able to provide written informed consent for the mother and her infant's study participation; in addition, when applicable the mother is willing and able to provide written assent for her and her infant's study participation.
- 4.2.1.2** At screening, evidence of a viable singleton pregnancy with gestational age of 32 weeks or less, defined as 224 days or less after the date of conception with sonographic confirmation \*
- 4.2.1.3** Within 14 days prior to study entry, negative by HIV RNA test.

*\*Note: if adequate sonographic results are not available from medical records at screening, an ultrasound must be performed in the interim so that the result is available at study entry.*

**4.2.1.4** At study entry, HIV rapid test negative and absence of symptoms of acute HIV infection (i.e. acute viral illness).

**4.2.1.5** At screening, Hepatitis B negative by Hepatitis B surface antigen test performed.

**4.2.1.6** At screening, has the following laboratory test results:

- Grade 1 or normal ( $<2.5 \times \text{ULN}$ ) ALT
- Grade 1 or normal ( $\geq 9.5 \text{ g/dL}$ ) HB
- Grade 1 or normal ( $\geq 800 \text{ cells/mm}^3$ ) ANC
- Normal ( $\geq 90 \text{ mL/min}$ ) for estimated creatinine clearance (CrCl; Cockcroft-Gault formula)

**4.2.1.7** At screening, mother has negative or trace proteinuria (less than Grade 1).

**4.2.1.8** At screening, mother has normal dipstick urine for glucose (less than Grade 1).

**4.2.1.9** Intention to stay within the study site's catchment area through 26 weeks postpartum

**4.2.1.10** Regular access to a cellular phone that is able to receive SMS messages, and for Cohort 1 only, is also able to send SMS messages.

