Laboratory	Blood	
Collect blood for:
 
 
HIV RNA test
 
Store plasma for HIV drug resistance testing
 
Rapid HIV test [see Section 6.3 in the event the test is (+)]
 
 
Weeks 4, 12:
 
 
ALT, Creatinine, and CrCl
 
 
Cohort 1 and Cohort 2/Step 2 only:
 
 
TFV-DP level (DBS)
 

	Other	
Collect vaginal swab once at EGA 34-38/40 weeks for:
 
 
Microbiome
 
 
Collect rectal swabs once at EGA 34-38/40 weeks (if consented) for:
 
 
Microbiome
 
 
Cohort 1 and Cohort 2/Step 2 only; collect at one visit at EGA 34-38/40 weeks:
 
 
Collect vaginal secretions for drug level
 

Study Drug		
Cohort 1 and Cohort 2/Step 2 only:
 
 
Prescribe and dispense study drug
 

### 6.2.1.3 PrEP Comparison Component Maternal Antepartum Week 24 and 36

Participants in both Cohort 1 and Cohort 2 who enroll early in gestation (i.e., prior to 20 weeks' gestation) may return for visits at AP Study Weeks 24 and 36. These visits are targeted to take place 168 and 252 days from the date of study entry (Day 0), respectively, with an allowable window of  $\pm$  14 days.

In addition to the standard of care HIV prevention package provided and routine safety evaluations for all study participants at these visits, assessments are conducted in the PrEP study cohort of PrEP acceptability and adherence.

Note that women who are selected for and consent to participation in the Qualitative In-Depth Interview during pregnancy may be scheduled for their interview at the time of their regular study visit at Week 24 or 36 or at an alternative date. See [Section 6.2.1.8](#) for details about this visit.

PrEP Comparison Component Maternal AP Week 24 and 36 Visit Procedures ( $\pm$ 14 days)	
Administrative and Regulatory	
 
Review locator information
 

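### The supplemental odds ratio for spontaneous abortion (SAP 6.3.3) has no at-risk restriction, so it depends on when women enrolled and started PrEP as well as on PrEP

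*SAP*

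**What the plan says.** **Entry.** Protocol 4.2.1 requires "evidence of a viable singleton pregnancy with gestational age of 32 weeks or less" and sets no lower limit. Protocol 6.2.1.3 treats women who enter before 20 weeks as a subgroup that may need extra antepartum visits, so entry is expected on both sides of 20 weeks.

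**Event.** SAP 6.3.3 defines the first component of the composite as "Spontaneous abortion (occurring at <20 weeks gestation").

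**Analysis.** The population summary in SAP 6.3.3 is the "Odds ratio of an adverse pregnancy outcome among PrEP exposed women during pregnancy", compared with women unexposed in pregnancy. The intercurrent-event list there includes Cohort 2/Step 2, so women who take up PrEP after enrolment can be in the exposed group. The supplemental analyses are univariable and multivariable logistic regressions, the latter "controlling for potential confounders", with no covariate named. Then: "The same analyses will be conducted for each of the pregnancy outcomes which comprise the" composite, one by one. One denominator rule follows: "Analyses of small-for-gestational age births will be restricted to live births". There is no matching rule for spontaneous abortion.

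**Analysis set and balance.** The Maternal Safety Set (SAP section 4) is all enrolled mothers, with no gestational-age limit. Cohort is chosen by the participant (Protocol 9.2.1). Enrolment balance is monitored by 1st or 2nd versus 3rd trimester (SAP 2.1.2). Stratification by gestational age at enrolment is stated for the maternal and infant adverse-event analyses (SAP 6.3.2 and 6.3.4), but not for pregnancy outcomes.

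**The concern.** The SAP confines small-for-gestational-age to births that can show it but does not apply the same principle to spontaneous abortion. Two kinds of women then enter the spontaneous abortion model with an outcome fixed in advance:

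- women enrolled at 20 to 32 weeks, in either cohort;
- Cohort 2 women who first start PrEP after 20 weeks, who are counted as exposed only because they have already passed the period of risk.

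The first kind distorts the odds ratio if the cohorts differ in the share enrolled before 20 weeks, which self-selection makes possible. The second moves the odds ratio towards apparent safety even when those shares are equal. What is at stake is a reported odds ratio for pregnancy loss, under a primary safety objective, that could differ from 1 for reasons unrelated to PrEP.

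**Working it through.** The documents give no figure for this analysis, so there is none to reproduce.

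**Inputs.** From the documents: 200 women in Cohort 1 and 100 in Cohort 2 (SAP 2.4.2), entry up to 32 weeks, event before 20 weeks. Assumed, because the documents give neither: *s*, the share of a group enrolled before 20 weeks, and *q*, the risk of spontaneous abortion among those women.

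**Formula.** With all women in the denominator, a group's risk is *s* × *q*, and OR = odds(*s*₁*q*₁) / odds(*s*₂*q*₂), where odds(*p*) = *p*/(1 − *p*). For a rare event this is close to the true OR × *s*₁/*s*₂.

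**1. Entry timing, no PrEP effect, *q* = 5% in both groups**

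| Enrolled before 20 weeks, exposed / unexposed | Risks | OR, all women | OR, at-risk women |
|---|---|---|---|
| 30% / 50% | 1.5% / 2.5% | (0.015/0.985)/(0.025/0.975) = 0.59 | 1.00 |
| 40% / 60% | 2.0% / 3.0% | 0.66 | 1.00 |
| 30% / 40% | 1.5% / 2.0% | 0.75 | 1.00 |
| 30% / 30% | 1.5% / 1.5% | 1.00 | 1.00 |
| 50% / 30% | 2.5% / 1.5% | 1.68 | 1.00 |

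Changing *q* to 2% or 10% barely alters this: 30% versus 40% gives 0.75 and 0.74.

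**2. A true effect.** Take a true OR of 2 with 5% risk in unexposed women. Equal shares of 40% give 1.94, a small attenuation. Shares of 20% versus 40% give 0.95.

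**3. Trimester monitoring.** Suppose 70% of each cohort enrols in the 1st or 2nd trimester, so the monitored factor is balanced. If 30% versus 50% enrol before 20 weeks, the OR is still 0.59.

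**4. Late PrEP start with equal enrolment.** Let 40% of each cohort enrol before 20 weeks, with *q* = 5% and no effect. Cohort 1 has 80 at-risk women and 4 events; Cohort 2 has 40 and 2. If 20 Cohort 2 women start PrEP after 20 weeks but before delivery, exposed is 4/220 and unexposed 2/80: OR = (4/216)/(2/78) = 0.72. Restricting to women enrolled before 20 weeks and counting late starters as unexposed restores 4/80 versus 2/40, OR 1.00.

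**5. Precision.** In the 30% / 50% scenario, expected events are 200 × 0.015 = 3.0 and 100 × 0.025 = 2.5. The variance of log OR is 1/3 + 1/197 + 1/2.5 + 1/97.5 = 0.749, so an approximate 95% Wald interval around 0.59 is 0.11 to 3.24.

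**6. The composite.** Combine 1.5% versus 2.5% with an assumed risk *a* from the other components, equal in both groups. Simple addition gives 16.5% versus 17.5% at *a* = 15% (OR 0.93) and 31.5% versus 32.5% at *a* = 30% (OR 0.96). Using 1 − (1 − *a*)(1 − *c*), with *c* the spontaneous abortion risk, gives 0.94 at 15% and 0.97 at 30%. The range is about 0.93 to 0.97.

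**The case against.** The strongest reply is that this is a minor analysis. It is one component of a supplemental analysis, with perhaps three events against two or three, and nobody could conclude much from the odds ratio with or without a restriction. Protocol 9.2.1 already says that power for safety conclusions is limited and that low event rates limit adjustment. That stands, and it limits how much the point matters.

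The imbalance is assumed. Protocol 9.2.5 names gestational period of enrolment as a bias risk and allows one cohort's enrolment to be curtailed. That also stands, but the monitored cut is by trimester and does not separate women before and after 20 weeks (step 3).

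The multivariable model might include gestational age at entry. It might, but the SAP does not say so, the univariable model would not, and an indicator for entry at 20 weeks or later would have no events in one level. Restriction is cleaner.

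The analysis-set, missing-data and analysis-approach cells of the 6.3.3 table are not fully legible in the text available, and the Analysis Implementation Plan is not among the documents, so a restriction there cannot be excluded. The supplemental paragraph carrying the only stated restriction is intact.

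A reader might infer that the primary composite is materially biased by the same route. Step 6 does not support that: the shift is a few per cent on the odds-ratio scale. Earlier truncation of other components, such as preterm delivery, would be a separate argument and is not sized here.

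**Conclusion.** The point holds for the component analysis. As written, the spontaneous abortion odds ratio mixes any PrEP effect with the timing of enrolment and of PrEP start. Under no effect and an assumed 5% risk it is 0.59 at 30% versus 50% enrolled before 20 weeks and 1.68 at the reverse. Twenty late starters alone give 0.72 with equal enrolment. If shares are equal and nobody starts late, it is close to unbiased.

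These sizes rest on assumed risks, enrolment shares and numbers of late starters. The documents do not show that the cohorts differ, so they do not support saying that the result is biased or in which direction. The late-start element also depends on grouping by exposure during pregnancy, as in SAP 6.3.3. Under grouping by original cohort, as in Protocol 3.2, only the entry-timing element remains.

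**What to change.** Add one sentence to the supplemental analyses in SAP 6.3.3, next to the small-for-gestational-age rule:

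*Analyses of spontaneous abortion will be restricted to women enrolled before 20 weeks' gestation, with PrEP exposure classified by whether PrEP was started before 20 weeks (or before the loss, if earlier); women who start PrEP at or after 20 weeks count as unexposed for this outcome.*

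The last clause matters. A simpler rule that required exposed women to have started before 20 weeks, and gave later starters no place, would drop women who were at risk, unexposed and event-free. With 50 Cohort 2 women enrolled early, 2.5 expected events and no effect, dropping 5 gives OR (0.05/0.95)/(2.5/42.5) = 0.89, and dropping 10 gives (0.05/0.95)/(2.5/37.5) = 0.79.

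Cost: one SAP sentence and a smaller denominator for one component, from which only women not at risk are removed. No new data are needed, since gestational age at entry and PrEP start are already collected. Differences in entry time within the group enrolled before 20 weeks remain; a delayed-entry analysis on the gestational-age scale would address them. Label: cheap improvement.
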